3. OVERALL STUDY DESIGN

3.1. Study Design

This study is a dose-finding prospective phase 1/1b, single arm, open-label, multi-institutional study to determine the MTD, DLT, safety, and preliminary efficacy of 16 weeks of IV ABI-009 treatment in patients with PAH who are WHO Functional Class II or III despite best available background therapy.

[figure not shown]
The study will be conducted in compliance with International Conference on Harmonisation (ICH) Good Clinical Practices (GCPs).

In phase 1, up to 24 patients will be enrolled using the standard 3+3 dose escalation design in the dose-finding phase.

In phase 1b, an additional 4-7 patients in up to 2 expansion cohorts to obtain a total of up to 10 patients at each of the 2 dose levels, MTD and/or an alternate dose or schedule. The MTD will be determined on the basis of the results from the safety evaluation. The RP2D, which may differ from the MTD, will be determined on the basis of results from safety, efficacy, and pharmacologic and correlative studies.

Patients who, in the opinion of the investigator and Safety Committee, tolerate ABI-009 well and achieve clinical benefit during the first **16-week Dose-finding Safety Part**, and for whom there are no alternative therapies available, may opt to continue therapy (**optional Extension Part**) for up to an additional 32 weeks at their assigned dose or lower, if permanently reduced. The optional Extension Part should start within 4 weeks after the last dose of the 16-week Dose-finding Safety Part.

Figure 9: Study Schema

3.2. Study Duration

The study was originally expected to take approximately 30 months from first patient enrolled to last patient follow-up, including approximately 18 months of enrollment period, up to 16 weeks of treatment (Dose-finding Safety Part) (or until treatment is tolerated), followed by an optional Extension Part for up to 32 additional weeks of ABI-009, and at least a 28 days follow-up after the last dose either in the Dose-finding Safety or Extension Part, whichever is later. With the addition of the 7.5 mg/m² dose cohort, it is anticipated that enrollment will take another 12 months for enrollment.

3.3. End of Study, End of Treatment, End of Treatment Visit, Follow-up Period

End of Study (EOS) is defined as either the date of the last visit of the last patient to complete the study, or the date of receipt of the last data point from the last patient that is required for primary, secondary, and/or exploratory analysis, as pre-specified in the protocol.

End of Treatment (EOT) is defined as the date of the last dose of ABI-009.

End of Treatment Visit is when safety and efficacy assessments and procedures are performed after the last treatment. For patients who complete the 16-week treatment, EOT visit occur at week 17 (± 3 days). For a patient who does not complete the 16-week treatment, EOT Visit must occur within 4 weeks (± 7 days) after the last dose of ABI-009.

Follow-up period is the on-study time period for at least 28 days after the last treatment either in the Dose-finding Safety Part or optional Extension Part, whichever is later. All patients that discontinue study drug and have not withdrawn full consent to participate in the study will continue in the follow-up phase for survival and therapy. Follow-up will continue up to 1 year approximately every 12 weeks (± 3 weeks), or more frequently as needed, until withdrawal of consent, or the study closes, whichever is the earliest. This evaluation may be made by record review and/or telephone contact.

4. STUDY POPULATION

4.1. Number of Patients

In phase 1: Up to 24 patients will be enrolled using the standard 3+3 dose escalation design.

In phase 1b: Additional 4-7 patients in up to 2 expansion cohorts to obtain a total of up to 10 patients at each of the 2 dose levels, MTD and an alternate dose or schedule.

4.2. Inclusion Criteria

- 1) Male or female age ≥ 18 years old with a current diagnosis of WHO Group 1 PAH including idiopathic pulmonary arterial hypertension (IPAH), heritable pulmonary arterial hypertension (HPAH), drug and toxin induced PAH, or PAH associated with connective tissue disease, or congenital heart defects (repaired greater than 1 year prior to Screening)
- 2) Must meet following hemodynamic definition prior to initiation of study drug
 - a. Mean PAP of ≥ 25 mmHg
 - b. PCWP or left ventricular end diastolic pressure (LVEDP) of ≤ 15 mm
 - c. PVR > 5 mmHg/L/min (Woods unit)
- 3) Functional class II or III according to the WHO set forth at the Dana Point Classification 2008 Meeting
- 4) On 2 or more specific standard PAH therapies (for ≥ 8 consecutive weeks and at stable dose for ≥ 4 consecutive weeks) unless documented inability to tolerate 2 standard therapies
- 5) Meet the following criteria determined by pulmonary function tests completed at screening:
 - a. Forced expiratory volume in one second (FEV1) $\geq 55\%$ of predicted normal
 - b. FEV1: forced vital capacity (FVC) ratio ≥ 0.60
- 6) 6MWD ≥ 150 meters and ≤ 450 meters
- 7) Male or non-pregnant and non-breast feeding female:
 - Females of child-bearing potential must agree to use effective contraception without interruption from 28 days prior to starting IP and while on study medication and have a negative serum pregnancy test (β -hCG) result at screening and agree to ongoing pregnancy testing during the course of the study, and after the end of study treatment. A second form of birth control is required even if she has had a tubal ligation.
 - Male patients must practice abstinence or agree to use a condom during sexual contact with a pregnant female or a female of childbearing potential while participating in the study. A second form of birth control is required even if he has undergone a successful vasectomy
- 8) Ability to provide written informed consent by the patient or legal guardian

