5. TABLE OF EVENTS

The schedule of assessments in [Table 2](#) outlines the specific time points for study assessments.

Table 2: Schedule of Assessments

Visit Days	Pre-Treatment	Study Treatment Monitoring During Up to 16 Weeks of Dose-finding Safety Part															End of Treatment Visit ^l	Optional Extension Part ^m	Safety Follow-up ⁿ		
Study Procedure ^a	Weeks on Intervention	Baseline Screening ^b	1	2	3	4	5	6	7	8	9	10	11	12	13	14	15	16	Week 17	Weekly, unless indicated	28 days after last dose, then Q12W
Informed Consent		x																			
Medical History/Demographics		x																			
I/E Criteria		x																			
Physical Exam		x	x	x	x	x	x	x	x	x	x	x	x	x	x	x	x	x	x	x	
Vital Signs, height, and weight ^c		x	x	x	x	x	x	x	x	x	x	x	x	x	x	x	x	x	x	x	
BSA ^d			x																		
Pregnancy Test ^e		x																x	E17, E33		
HIV and hepatitis tests		x																			
CBC/Differential/Chemistry		x	x	x	x	x	x	x	x	x	x	x	x	x	x	x	x	x	Every 2 weeks (E2-E32)		
NT Pro-BNP		x				x			x			x			x			x	E9, 17, 25, 33		
CRP		x				x			x			x			x			x			
Troponin		x				x			x			x			x			x			
Biomarker ^f		x																x			
Fasting Lipids		x				x			x			x			x			x	Every 4 weeks (E5-E29)		
Sirolimus level – central assays ^g			x	x	x	x															
Sirolimus level – local assays ^g			x	x	x	x	x	x	x	x	x	x	x	x	x	x	x	Every 2 weeks (E2-E32)			
Echocardiogram ^h		x				x			x			x			x			x			
6-minute walk distance		x				x			x			x			x			x			
WHO Function Class		x				x			x			x			x			x	E9, 17, 25, 33		
Pulmonary function test		x				x			x			x			x			x			
Right heart catheterization ⁱ		x															x ⁱ				
ABI-009 administration ^j			x	x	x	x	x	x	x	x	x	x	x	x	x	x	x	x	x		
Concomitant meds		x	x	x	x	x	x	x	x	x	x	x	x	x	x	x	x	x	x	x	x
Adverse event assessment ^k		Continuous, starting from signing of Informed Consent until 28 days after last dose of study drug																			
SF-36 and emPHasis10 QNR		x															x	E17, E33			

- ^a All visits are allowed to occur in a window of ± 3 days unless otherwise specified.
- ^b Baseline screening visit will be done within 28 days prior to study treatment Day 1.
- ^c Height measurement is only required at screening.
- ^d BSA will be calculated at week 1 and recalculated if the weight changes by $>10\%$.
- ^e Serum pregnancy test will be conducted at screening, urine pregnancy test will be conducted at week 17 or at the end of treatment visit.
- ^f Blood sample will be taken and stored for biomarker testing for patients who consent.

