- ^g Sirolimus levels for central labs are done for patients in dose-finding phase of the study: week 1 predose, immediately after termination of infusion (end infusion), then 1, 2, and 4 hrs post infusion, and predose at weeks 2, 3, 4. Local labs for trough levels (predose) of sirolimus from week 2 and thereafter are done for all treated patients (in both Dose-finding Safety and Extension Part). An optional PK evaluation via local lab at weeks 1 and 3 (at 24, 48, and 72 hrs) are done for patients who consent in the Dose-finding Safety Part.
- ^h Echocardiogram studies will follow the Echo Core Lab Manual and will be uploaded to central lab for analysis.
- ⁱ RHC will be submitted to centralized core labs for analysis and is optional for patients who do not complete the 16-week treatment but opt to have RHC performed.
- ^j ABI-009 must be administered after all study specific assessments are done in a visit.
- ^k Continuous, starting from signing of Informed Consent until 28 days after last dose of study drug
- ^l End of Treatment Visit for patients who do not complete the 16-week treatment must be within 4 weeks of last study treatment (± 7 days).
- ^m Optional Extension Part is for patients who tolerated ABI-009 well and showed clinical benefit during the Dose-finding Safety Part based on the opinion of the investigator and Safety Committee. This Extension Part should start within 4 weeks after the last dose of ABI-009 in the Dose-finding Safety Part. ABI-009 will be given at the originally assigned dose (or lower if reduced) for a maximum of 32 additional weeks, followed by an evaluation on week 33 for select assessments: urine pregnancy test, NT Pro-BNP, 6MWD, WHO functional class assessment, pulmonary function test, and SF-36 and emPHasis10 questionnaires. If treatment discontinues prior to week 32, the week 33 assessments should be done within 4 weeks of last treatment.
- ⁿ Safety follow-up will continue for a minimum of 28 days then approximately every 12 weeks (± 3 weeks) by phone call after the last treatment either in the Dose-finding Safety Part or optional Extension Part. Follow-up will continue up to 1 year approximately every 12 weeks (± 3 weeks), or more frequently as needed, until withdrawal of consent, or the study closes, whichever is the earliest.

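### No pregnancy test is scheduled between screening and week 17, so all 16 weekly infusions can be given without one, although eligibility calls for ongoing testing

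*Combined protocol and SAP*

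**What the plan says.** Criterion 7 in Section 4.2 requires a negative serum test at screening and asks each woman of child-bearing potential to "agree to ongoing pregnancy testing during the course of the study, and after the end of study treatment". It gives no frequency.

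The schedule is in Section 5:

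- **Dose-finding Safety Part.** Table 2, note e: "Serum pregnancy test will be conducted at screening, urine pregnancy test will be conducted at week 17 or at the end of treatment visit". Note b: "Baseline screening visit will be done within 28 days prior to study treatment Day 1". Note a: "All visits are allowed to occur in a window of" ±3 days unless otherwise specified. The weekly list (6.2.1) and the list for weeks 5, 9 and 13 (6.2.2) contain no pregnancy test. Table 3 names the test as an analyte but gives it no time point.
- **Early stoppers.** Section 3.3: "For a patient who does not complete the 16-week treatment, EOT Visit must occur within 4 weeks" (±7 days) of the last dose.
- **Extension Part.** Table 2 lists tests at E17 and E33. Note m describes up to 32 weeks of treatment "followed by an evaluation on week 33 for select assessments: urine pregnancy test". It adds: "If treatment discontinues prior to week 32, the week 33 assessments should be done within 4 weeks of last treatment". On timing it says: "This Extension Part should start within 4 weeks after the last dose of ABI-009 in the Dose-finding Safety Part". Section 6.6 lists no pregnancy test at all.

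Women must use contraception from 28 days before the first dose and for as long as they take study drug, with a second method. No period after the last dose is stated. Section 11.4 asks investigators to watch for pregnancies for 3 months after it.

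**The concern.** The trial admits only non-pregnant women and gives an mTOR inhibitor every week. Criterion 7 has the patient agree to repeated testing during the study, yet the schedule places no test inside the first 16 weeks of dosing and only one (E17) inside the Extension. A site that does exactly what Table 2 asks has no planned means of finding a pregnancy while infusions continue.

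Two statements elsewhere in the protocol add weight. Section 1.1 describes a disease that affects women about twice as often as men, with a mean age at diagnosis of 36, so women of child-bearing potential may form a good part of enrolment. Section 9.1 urges caution with hormonal contraceptives because a metabolic interaction has not been excluded, so one common form of the main safeguard is itself uncertain.

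What is at stake is unintended exposure in pregnancy. The documents give no embryo-fetal data for ABI-009 (Section 11.1 refers to package inserts), so no size of fetal risk is claimed.

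**Working it through.** The plan states no figure to reproduce. The check is a count of scheduled tests and day arithmetic.

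**Inputs.** Screening up to 28 days before Day 1 (note b); 16 weekly infusions (6.2); end-of-treatment visit for early stoppers up to 28 days after the last dose, +7 (3.3); Extension start up to 28 days after the last dose (note m); visit window ±3 days (note a). Set Day 1 = 0. Dose k then falls on day 7(k − 1), dose 16 on day 105, and week 17 on day 112.

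**Current gaps between scheduled tests**

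| Interval | Days | Infusions |
|---|---|---|
| Screening to week 17 | 28 + 112 = 140 (143 with +3) | 16 |
| Screening to end-of-treatment visit, stopped after dose 15 | 28 + 98 + 28 = 154 (161 with +7) | 15 |
| Week 17 to E17 | 112 to 133 | 16 |
| Week 17 to final assessment, latest Extension start, stopped after E16 | 21 + 105 + 28 = 154 | 16 |
| E17 to E33 | 112 | 16 |

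The upper value of 133 arises because E1 can be as late as day 105 + 28 = 133, which is 21 days after week 17, and 21 + 112 = 133. A woman who completes 48 weeks has 4 scheduled tests.

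**Average exposure, given a conception during the 16-week part.** Assume that the time of conception is uniform over the 112 dosing days and that only a scheduled test detects it. The dose on day d follows the conception with probability d/112. The mean number of infusions after conception is (0 + 7 + … + 105)/112 = 840/112 = 7.5.

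**With tests on days 0, 28, 56, 84 and 112**, each before that day's dose:

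- *Positive at once (lag 0).* The mean within a 28-day interval is (0 + 7 + 14 + 21)/28 = 1.5.
- *Lag of 7 days.* One quarter of conceptions miss the next test. In the first three of the four intervals this adds 4 infusions; in the last it adds none, because dosing in this part has ended. Mean: 1.5 + (3/4)(1/4)(4) = 2.25.
- *Lag of 14 days.* One half miss the next test. Mean: 1.5 + (3/4)(1/2)(4) = 3.0.

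**Intervals after the change.** In the 16-week part they are 28 days and 4 infusions (28 + 3 + 3 = 34 days with windows). In the Extension, with tests at E1, E9, E17, E25 and E33, they are 56 days and 8 infusions (56 + 6 = 62 with windows). Early stoppers can have a longer last interval without extra infusions. Stopping after dose 12 gives 77 + 28 − 56 = 49 days (56 with +7). Stopping after E24 gives 161 + 28 − 112 = 77 days.

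**Contraception after the last dose.** Section 1.2.3.7 gives a terminal half-life of 40 to 91 hours. Assuming this holds at 1 to 7.5 mg/m², five half-lives are 200 to 455 hours, or 8.3 to 19.0 days. The drug therefore persists after the last infusion, but for much less than 3 months.

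**The case against.** The best case for the plan is that nothing is contradicted. Criterion 7 obtains an agreement and sets no frequency, Table 2 sets the dates, and sites may test more often. Contraception covers the whole screening window, a second method is required, and patients are seen weekly with an examination and adverse event review. Exposure to all 16 infusions needs a conception between screening and Day 1 despite all this. The average of 7.5 is conditional on a conception and assumes nobody notices it before the scheduled test.

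The event would also be rare. As an illustration, take 32 patients (24 plus 4 in each of two expansions), about 21 women from the 2:1 ratio, all of child-bearing potential, an assumed dual-method failure rate of 0.1% to 1% per year, and 140 days. The expected number of pregnancies is 21 × 0.001 × 140/365 ≈ 0.008, up to about 0.08.

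Much of this stands. The 16-infusion case is the extreme, 7.5 is an upper figure if symptoms prompt earlier testing, and the expected count is low. None of it supplies a test: permission to test more is not a requirement, and zero tests during 16 weeks of dosing is hard to call ongoing.

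Three smaller objections also have substance:

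- The 3-month window in Section 11.4 is for reporting and need not equal a contraception period. The consent pages, which were not available, may state one.
- The proposed Extension interval is twice that of the first part, although dosing is weekly in both.
- The week 17 and E33 tests meet the requirement for testing after treatment, but they come only about 7 days after the last dose in completers. They are too early to show a conception around that dose, and the proposed tests do not change this.

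**Conclusion.** The concern holds. The schedule leaves the 16-week dosing period untested and puts one test inside the 32-week Extension, against a criterion that asks for ongoing testing. The nominal gap is 140 days and 16 infusions. The average of 7.5 infusions, against 1.5 to 3.0 after the change, rests on uniform timing of conception, detection by scheduled test only, and a lag of 0 to 14 days.

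The contraception point is accurate but secondary, because the documents do not determine how long the period after the last dose should be. This is worth correcting because the remedy is cheap, not because many pregnancies are expected. It does not bear on dose finding or on any analysis.

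**What to change.** Amend Table 2 and note e to add urine pregnancy tests for women of child-bearing potential, before dosing:

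- on Day 1, unless the screening test was done within the 72 hours that Section 6.2.1 already allows;
- at weeks 5, 9 and 13;
- at E1, E9 and E25, where a week 17 test on the same day counts as E1.

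Add the same tests to Sections 6.2.1, 6.2.2 and 6.6, and bring the existing E17 and E33 tests into 6.6. If the sponsor wants 4-weekly testing in the Extension too, the lipid visits E5 to E29 can carry it, with seven added Extension tests (E1, E5, E9, E13, E21, E25, E29) in place of three.

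Extend women's contraception in criterion 7 to a stated period after the last dose. Three months would match Section 11.4; a shorter period justified from the half-life would also close the gap.

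**Cost.** Amendment wording and up to 7 inexpensive urine tests per woman over 48 weeks (4 in the first part, 3 in the Extension), taking the total from 4 to at most 11. All fall at visits already planned for dosing. Women take on more tests and a longer contraception commitment.

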4.3. Exclusion Criteria

A patient will not be eligible for inclusion in this study if any of the following criteria apply:

- 1) History of heart disease including left ventricular ejection fraction (LVEF) $\leq 40\%$ or clinically significant valvular constrictive or atherosclerotic heart disease (myocardial infarction, angina, cerebrovascular accident)
- 2) History of malignancy in 2 years prior to enrollment
- 3) Pulmonary hypertension (PH) belonging to groups 2 to 5 of the 2013 Nice classification
- 4) Current or recent (<3 months) use of intravenous inotropic or vasopressor agents for the treatment of PAH
- 5) Recent (<2 months) PAH-related hospital admission
- 6) History of allergic reactions attributed to compounds of similar chemical or biologic composition including macrolide (eg, azithromycin, clarithromycin, dirithromycin, and erythromycin) and ketolide antibiotics
- 7) Uncontrolled diabetes mellitus as defined by HbA1c $> 8\%$ despite adequate therapy
- 8) Uncontrolled hyperlipidemia (serum triglyceride ≥ 300 mg/dL)
- 9) Serum cholesterol ≥ 350 mg/dL
- 10) Surgery within 3 months of start date of study drug
- 11) Baseline cytopenias:
 - a. Absolute Neutrophil Count $\leq 1.5 \times 10^9/L$
 - b. Hemoglobin ≤ 9 g/dL
 - c. Platelet count $\leq 100,000/mm^3$
- 12) Baseline liver disease: ALT/AST, total bilirubin, alkaline phosphatase $\geq 1.5 \times$ ULN
- 13) Creatinine clearance (Cockcroft formula) ≤ 30 mL/min
- 14) Inability to attend scheduled clinic visits
- 15) Prior use of an mTOR inhibitor within previous 6 months from enrollment
- 16) Previous lung transplant
- 17) Known Human Immunodeficiency Virus (HIV)
- 18) Active Hepatitis B or Hepatitis C
- 19) Uncontrolled intercurrent illness that in the opinion of the investigator would limit compliance and tolerance to study requirements (eg, ongoing or active infection, symptomatic congestive heart failure, unstable angina pectoris, cardiac arrhythmia, diabetes, uncontrolled hypertension, coronary artery disease, or psychiatric illness/social situations)
- 20) Concomitant enrollment in another investigational treatment protocol for PAH
- 21) Use of strong inhibitors and inducers of CYP3A4 within the 14 days prior to receiving the first dose of ABI-009. Additionally, use of any known CYP3A4 substrates with narrow therapeutic window (such as fentanyl, alfentanil, astemizole, cisapride, dihydroergotamine, pimozide, quinidine, terfanide) within the 14 days prior to receiving the first dose of ABI-009

5. TABLE OF EVENTS

The schedule of assessments in [Table 2](#) outlines the specific time points for study assessments.

Table 2: Schedule of Assessments

Visit Days	Pre-Treatment	Study Treatment Monitoring During Up to 16 Weeks of Dose-finding Safety Part															End of Treatment Visit ^l	Optional Extension Part ^m	Safety Follow-up ⁿ		
Study Procedure ^a	Weeks on Intervention	Baseline Screening ^b	1	2	3	4	5	6	7	8	9	10	11	12	13	14	15	16	Week 17	Weekly, unless indicated	28 days after last dose, then Q12W
Informed Consent		x																			
Medical History/Demographics		x																			
I/E Criteria		x																			
Physical Exam		x	x	x	x	x	x	x	x	x	x	x	x	x	x	x	x	x	x	x	
Vital Signs, height, and weight ^c		x	x	x	x	x	x	x	x	x	x	x	x	x	x	x	x	x	x	x	
BSA ^d			x																		
Pregnancy Test ^e		x																x	E17, E33		
HIV and hepatitis tests		x																			
CBC/Differential/Chemistry		x	x	x	x	x	x	x	x	x	x	x	x	x	x	x	x	x	Every 2 weeks (E2-E32)		
NT Pro-BNP		x				x			x			x			x			x	E9, 17, 25, 33		
CRP		x				x			x			x			x			x			
Troponin		x				x			x			x			x			x			
Biomarker ^f		x																x			
Fasting Lipids		x				x			x			x			x			x	Every 4 weeks (E5-E29)		
Sirolimus level – central assays ^g			x	x	x	x															
Sirolimus level – local assays ^g			x	x	x	x	x	x	x	x	x	x	x	x	x	x	x	Every 2 weeks (E2-E32)			
Echocardiogram ^h		x				x			x			x			x			x			
6-minute walk distance		x				x			x			x			x			x			
WHO Function Class		x				x			x			x			x			x	E9, 17, 25, 33		
Pulmonary function test		x				x			x			x			x			x			
Right heart catheterization ⁱ		x															x ⁱ				
ABI-009 administration ^j			x	x	x	x	x	x	x	x	x	x	x	x	x	x	x	x	x		
Concomitant meds		x	x	x	x	x	x	x	x	x	x	x	x	x	x	x	x	x	x	x	x
Adverse event assessment ^k		Continuous, starting from signing of Informed Consent until 28 days after last dose of study drug																			
SF-36 and emPHasis10 QNR		x															x	E17, E33			

- ^a All visits are allowed to occur in a window of ± 3 days unless otherwise specified.
- ^b Baseline screening visit will be done within 28 days prior to study treatment Day 1.
- ^c Height measurement is only required at screening.
- ^d BSA will be calculated at week 1 and recalculated if the weight changes by $>10\%$.
- ^e Serum pregnancy test will be conducted at screening, urine pregnancy test will be conducted at week 17 or at the end of treatment visit.
- ^f Blood sample will be taken and stored for biomarker testing for patients who consent.
- ^g Sirolimus levels for central labs are done for patients in dose-finding phase of the study: week 1 predose, immediately after termination of infusion (end infusion), then 1, 2, and 4 hrs post infusion, and predose at weeks 2, 3, 4. Local labs for trough levels (predose) of sirolimus from week 2 and thereafter are done for all treated patients (in both Dose-finding Safety and Extension Part). An optional PK evaluation via local lab at weeks 1 and 3 (at 24, 48, and 72 hrs) are done for patients who consent in the Dose-finding Safety Part.
- ^h Echocardiogram studies will follow the Echo Core Lab Manual and will be uploaded to central lab for analysis.
- ⁱ RHC will be submitted to centralized core labs for analysis and is optional for patients who do not complete the 16-week treatment but opt to have RHC performed.
- ^j ABI-009 must be administered after all study specific assessments are done in a visit.
- ^k Continuous, starting from signing of Informed Consent until 28 days after last dose of study drug
- ^l End of Treatment Visit for patients who do not complete the 16-week treatment must be within 4 weeks of last study treatment (± 7 days).
- ^m Optional Extension Part is for patients who tolerated ABI-009 well and showed clinical benefit during the Dose-finding Safety Part based on the opinion of the investigator and Safety Committee. This Extension Part should start within 4 weeks after the last dose of ABI-009 in the Dose-finding Safety Part. ABI-009 will be given at the originally assigned dose (or lower if reduced) for a maximum of 32 additional weeks, followed by an evaluation on week 33 for select assessments: urine pregnancy test, NT Pro-BNP, 6MWD, WHO functional class assessment, pulmonary function test, and SF-36 and emPHasis10 questionnaires. If treatment discontinues prior to week 32, the week 33 assessments should be done within 4 weeks of last treatment.
- ⁿ Safety follow-up will continue for a minimum of 28 days then approximately every 12 weeks (± 3 weeks) by phone call after the last treatment either in the Dose-finding Safety Part or optional Extension Part. Follow-up will continue up to 1 year approximately every 12 weeks (± 3 weeks), or more frequently as needed, until withdrawal of consent, or the study closes, whichever is the earliest.

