2.2. Primary Endpoints

- Dose finding phase: Establish the MTD, DLT, and safety of 16 weeks of ABI-009 given IV
- Safety profile of the up to 48 weeks of treatment

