6.3. End of Treatment Visit Assessment

End of Treatment Visit assessment for a patient is when efficacy and safety assessments and procedures are performed after the last treatment in the 16-week Dose-finding Safety Part. For patients who complete the 16-week treatment, EOT assessments occur on week 17 (± 3 days) and for patients who do not complete the 16-week treatment, EOT assessments must occur within 4 weeks (± 7 days) after the last dose of ABI-009.

- Physical exams, vital signs, and weight
- Complete blood count with differential and chemistry panel
- Concomitant medications
- Adverse Events
- Urine pregnancy
- NT Pro-BNP
- CRP
- Troponin
- Biomarker analysis (optional)
- Fasting lipids
- Echocardiogram
- 6MWD test
- WHO Functional Class
- Pulmonary function test
- Right heart catheterization

- SF-36 and emPHasis10 questionnaire

For patients who fail to complete the 16-week treatment, RHC can be performed if patients opt to have the procedure. RHC results from these patients will be analyzed separately from those of patients who complete the 16-week treatment.

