6.6. Assessments During the Optional Extension Part

For patients who tolerated ABI-009 well and showed clinical benefit during the Dose-finding Safety Part, based on the investigator and Safety Committee's judgement can continue treatment for up to an additional 32 weeks. All assessments must be done prior to dosing:

Every visit when ABI-009 is given (E1 through E32):

- Physical exams
- Vital signs and weight
- Concomitant medications

Every 2 visits when ABI-009 is given from E2 through E32:

- Complete blood count with differential and chemistry panel

Sirolimus Every 4 weeks when ABI-009 is given (E5 through E29):

- Lipids

Every 8 weeks (ie, at weeks E9, E17, E25, and E33):

- 6MWD test
- WHO Functional Class
- Pulmonary function test
- NT Pro-BNP

Every 16 weeks (ie, at weeks E17 and E33):

- SF-36 and emPHasis10 questionnaire

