All AEs will be recorded by the investigator from the time the patient signs informed consent until 28 days after the last dose of ABI-009 and those SAEs made known to the investigator at any time thereafter that are suspected of being related to IP. AEs and SAEs will be recorded on the AE page of the eCRF and in the patient's source documents. All SAEs must be reported to Aadi Drug Safety within 24 hours of the investigator's knowledge of the event by facsimile, or other appropriate method, using the SAE Report Form, or approved equivalent form.

The investigator's clinical judgment is used to determine whether a patient is to be removed from treatment due to an AE. The investigator is responsible for ensuring that all AEs observed by the investigator or reported by the patient that occur after the first dose of IP through the EOT Visit are reported using the applicable eCRF (eg, AE Summary CRF).

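### No physical exam, vital signs, blood count, chemistry or fasting lipids are scheduled after the last Extension infusion, so asymptomatic laboratory toxicity and recovery in the following 28 days are not systematically looked for

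*Combined protocol and SAP*

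**What the plan says.** Section 2.2 makes this a primary endpoint: "Safety profile of the up to 48 weeks of treatment". Section 11.1 has the investigator record adverse events "until 28 days after the last dose of ABI-009".

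Section 6.3 describes the End of Treatment Visit as one "performed after the last treatment in the 16-week Dose-finding Safety Part". Its list includes physical exam, vital signs, weight, blood count with differential, chemistry and fasting lipids.

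For the Extension, Section 5, Table 2 note m gives up to 32 more weeks of treatment, "followed by an evaluation on week 33 for select assessments: urine pregnancy test, NT Pro-BNP, 6MWD, WHO functional class assessment, pulmonary function test", together with the SF-36 and emPHasis10. For early stops it adds: "If treatment discontinues prior to week 32, the week 33 assessments should be done within 4 weeks of last treatment".

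Section 6.6 sets the rest of the Extension schedule:
- Exam, vital signs and weight: "Every visit when ABI-009 is given (E1 through E32").
- Blood count and chemistry: "Every 2 visits when ABI-009 is given from E2 through E32".
- Lipids: every 4 weeks, E5 to E29.
- Order within a visit: "All assessments must be done prior to dosing".

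For the Safety Follow-up column, Table 2 shows concomitant medication and the continuous adverse event row. Note n describes the contacts every 12 weeks as phone calls.

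**The concern.** The protocol provides post-treatment safety tests in its shorter part and omits them in its longer one. A laboratory adverse event without symptoms is recorded only if someone draws a sample. In the Extension, every scheduled safety sample comes before an infusion, so none shows the effect of the last one. The visit that follows measures function, NT Pro-BNP and quality of life, but not counts, chemistry or lipids.

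At stake is the late end of the safety record. New asymptomatic cytopenia or liver, renal or lipid changes after the last dose would be under-ascertained relative to the 16-week part. Recovery of abnormalities present at the last dosing visit would have no scheduled documentation. Event rates from the two parts would then rest on different post-dose ascertainment.

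**Working it through.** **Step 1. The plan's own figure.** Dose-finding Safety Part 16 weeks + Extension 32 weeks = 48 weeks, which agrees with Section 2.2. The Extension therefore falls within the primary safety endpoint.

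**Step 2. The two closing visits side by side.**

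| Item | Closing visit, 16-week part (6.3) | Last scheduled dosing-visit test, Extension (6.6, Table 2) | E33 or early-stop visit (note m, 6.6) |
|---|---|---|---|
| Physical exam, vital signs, weight | yes | E32, pre-dose | no |
| Blood count, chemistry | yes | E32, pre-dose | no |
| Fasting lipids | yes | E29, pre-dose | no |
| Urine pregnancy test | yes | not applicable | yes |
| NT Pro-BNP, 6MWD, functional class, PFT | yes | not applicable | yes |
| SF-36, emPHasis10 | yes | not applicable | yes |

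**Step 3. Count for a patient who completes E32.**
- Blood count and chemistry from E2 to E32 in steps of 2: (32 − 2)/2 + 1 = 16 samples.
- Lipids from E5 to E29 in steps of 4: (29 − 5)/4 + 1 = 7 samples.
- Every one of these is pre-dose. With the last infusion as day 0, E33 is day 7 and adverse event collection ends on day 28.
- Scheduled exams, blood counts, chemistries or lipid tests after the last infusion and up to day 28: **0**.

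**Step 4. Count for a patient who stops early.** The same E33 list applies, no later than 4 × 7 = 28 days after the last dose. It contributes 0 scheduled safety tests. The exception is a patient who attends a dosing visit, has a pre-dose count and is not dosed: that count falls after the last infusion.

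**Step 5. Is there exposure in the untested period?** Section 1.2.3.7 gives a terminal half-life of 40 to 91 hours. Five half-lives are 5 × 40/24 = 8.3 days to 5 × 91/24 = 19.0 days. On those figures exposure continues into the untested period. They come from oncology patients at 45 to 150 mg/m², so applying them here is an assumption.

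**Step 6. Effect of the change.** With safety tests added at E33 (day 7), the scheduled post-dose time points for a completer rise from 0 to 1. The longest stretch of the 28-day window without a scheduled test falls from 28 days to 28 − 7 = 21 days.

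**Step 7. The related inconsistency.** Sections 3.3 and 6.3 place the End of Treatment Visit, for patients who stop the 16-week part early, within 4 weeks ±7 days of the last dose. That allows day 28 + 7 = 35. Section 11.1 ends adverse event recording at day 28 in one sentence and at the End of Treatment Visit in another.

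**The case against.** The strongest reply is that much would still be seen. Adverse events are collected continuously to day 28, serious events are followed to resolution (synopsis, Key Safety Assessments), and Section 11.1 allows laboratory findings to form part of monitoring. Abnormalities present at E32 are already on record. This stands as a limit on the claim. A reader might infer that late laboratory toxicity cannot be detected at all, or that the record will necessarily look clean. The documents do not support that. Permission to test is not a schedule, however, so the narrower point survives.

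A reader might also infer that patients who stop for toxicity are the worst served. The documents do not support that either. They get the same closing list as completers. Section 7.2.1 requires neutrophil, platelet and hemoglobin criteria to be met before dosing, with a hold of up to 14 days until they are, so a patient held for a failed count has at least that count and probably repeats. Those criteria do not cover chemistry or lipids, and the hold concerns patients waiting to be re-dosed.

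Longer gaps can be computed: 21 + 28 = 49 days since the last lipids at E29, and 7 + 28 = 35 days since the last count for a last dose at an odd visit from E3. Both include time before the last dose. The 35 days also assumes no count at odd visits, whereas the synopsis describes weekly laboratory monitoring on infusion days and Section 7.2.1 sets per-dose criteria. Those passages do not match the two-weekly counts of Section 6.6 and need reconciling. The defensible figure is 28 days.

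The phase 1 rates in Section 1.2.3.6 (for example thrombocytopenia 58%, hypokalemia 23%) should not be read as expected rates here. They come from cancer patients at 45 to 150 mg/m², while the highest dose here is 7.5 mg/m², or 7.5/45 = one sixth of that study's lowest. The same section reports common non-laboratory events, such as mucosal inflammation 38% and fatigue 27%. Extension patients are also selected for tolerating the drug.

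It can further be said that Section 2.2 speaks of weeks of treatment, and that the 28 days are an adverse event collection rule and not a defined endpoint window. That is fair. Even so, events in those days are collected, and no scheduled safety test supports them.

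Finally, Section 3.3 defines the End of Treatment Visit in general terms, but gives timing only for the 16-week treatment, and Section 6.3 ties it to that part. Some rows of Table 2 are misaligned in the text available, so the finding rests mainly on note m and Section 6.6.

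**Conclusion.** The point holds as a gap in scheduled ascertainment. For every patient whose treatment ends in the Extension, the closing visit contains no safety tests. For a completer, 0 are scheduled in the 28 days after the last dose. Asymptomatic laboratory toxicity and recovery are therefore not systematically looked for at the end of a period covered by a primary safety endpoint, although the 16-week part has such a visit.

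This rests on two assumptions: that note m's list for E33 is complete, and that Section 6.6 ties exams and vital signs to dosing visits, as its wording says. The documents do not allow an estimate of how many events would be missed, and none is offered.

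On the side issue, a reader might infer that a day-35 End of Treatment Visit falls after adverse event collection has closed. Section 11.1 also runs reporting to that visit, so this is a contradiction to reconcile and not a settled closure. The Extension early-stop visit, at no more than 4 weeks, does not raise it.

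The change should be made, as an inexpensive improvement.

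**What to change.** In Table 2, note m and Section 6.6, add physical exam, vital signs and weight, blood count with differential, chemistry and fasting lipids to week E33 and to the early Extension-discontinuation visit that replaces it, so that both match the safety items in Section 6.3.

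Separately, reconcile the two adverse event end points in Section 11.1 with each other and with the 4 weeks ±7 days allowed for the End of Treatment Visit of patients who stop the 16-week part early.

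The cost is amendment wording and one set of routine tests at a visit the patient already attends and at which blood is already drawn for NT Pro-BNP. No visits or patients are added. A few more laboratory adverse events will probably be reported.
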